### 8.2.2. Summary Measure

Each HRCT scan will be conducted at two lung volumes: total lung capacity (TLC) and functional residual capacity (FRC); these will be referred to as scan conditions. The HRCT images will be processed to derive the HRCT parameters at FRC and TLC, however these conditions are not applicable for all parameters.

The HRCT scans will be conducted at Screening, Day 12 and Day 28. The 3 HRCT images will then be processed to derive the HRCT parameters at each scan; this data will be referred to as the untrimmed data. The untrimmed data measures all airways that are present in each scan.

However partially due to positioning of subjects whilst taking a scan, it can be that some airways are visible in some scans and not in other scans. For these reasons, some HRCT

imaging endpoints will be calculated to include only airways that are visible in both scans. Therefore, the scans were grouped into three scan trimming pairs where, within each scan trimming pair, the airways that were not present in both scans were removed/trimmed.

The three scan trimming pairs, and subsequent timepoints, are:

- The scan trimming pair SCRD28, which contains the Screening (SCRD28:SCR) and Day 28 (SCRD28:D28) timepoints, where only airways that were present in both screening and day 28 scans are accounted for.
- The scan trimming pair SCRD12, which contains the Screening (SCRD12:SCR) and Day 12 (SCRD12:D12) timepoints where only airways that were present in both screening and day 12 scan are accounted for.
- The scan trimming pair (D12D28), which contains the Day 12 (D12D28:D12) and Day 28 (D12D28:D28) timepoints, where only airways that were present in both day 12 and day 28 scans are accounted for.

These 6 HRCT images were then processed to derive the HRCT parameters at each of these scan-trimming pair time points; this data will be referred to as the scan trimmed data. The scan trimmed data considers only airways that were present in both scans within the scan trimming pair. This ensures the airway models are the same length although the cross-sectional area of the airway may vary. For example, the schematic below shows visible airways on Screening alone and Day 12 alone. It then shows the airways that are visible on both Screening & Day 12 scans, through removing/trimming airways that are not present in both scans.

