#### 8.3.2. Summary Measure

The structure of HRCT endpoints is as described in Section 8.2.2, exploratory endpoints include:

- iVlobe
- Percent Predicted iVlobe
- IALD
- LAS
- AT
- BVD
- iVaww
- siVaww

For all endpoints, the data will be inspected prior to analyses to determine whether a data transformation is required. Appropriate transformations will be applied prior to summaries and statistical analyses. It is likely a log transformation will be required for iVlobe, LAS, IALD, BVD iVaww and siVaww, and that no transformation will be required for Percent Predicted iVlobe and AT, however, the most appropriate distribution should be used

Summary statistics will be presented for absolute data and change from baseline. Separate statistical models will be fitted for each scan trimming condition (Untrimmed or Scan Trimmed), lung volume (FRC or TLC) and Regions (Upper, Lower, Central, Distal and Total) combination as appropriate, note: statistical analyses will only be conducted on:

- IALD for upper and lower regions only (within the same model)
- LAS at TLC for total region only
- AT at FRC for total region only
- BVD at TLC for total region only
- siVaww untrimmed data at TLC for distal region only

For the endpoints: LAS, AT and BVD, separate statistical models will be fitted for the Total region only. The change from baseline (accounting for the average baseline associated to the region) will be represented via adjusted posterior medians for each of the Treatment Arms, as well as their associated 95% HPD-tailed credible intervals. These results will also be presented within tabular form, and will be presented after the data have been appropriately back transformed (if applicable). The difference between the treatment arms, for the change from baseline will be represented via adjusted medians, as

well as their associated 95% HPD-tailed credible intervals. These results will also be presented in tabular form, and will be presented after the data have been appropriately back transformed to give median ratios (or median differences if applicable).

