For the endpoint IALD, a statistical model will be fitted for both the Upper and Lower regions. The change from baseline across the different regions (accounting for the average baseline associated to the region of interest) will be represented via adjusted posterior medians for each of the Treatment Arms, as well as their associated 95% HPD-tailed credible intervals. These results will also be presented within tabular form, and will be presented after the data have been appropriately back transformed (if applicable). The difference between the treatment arms, for the change from baseline across the different regions will be represented via adjusted medians, as well as their associated 95% HPD-tailed credible intervals. These results will also be presented in tabular form, and will be presented after the data have been appropriately back transformed to give median ratios (or median differences if applicable).

For the endpoint siVaww, a statistical model will be fitted for the distal region using untrimmed data. The change from baseline (accounting for the average baseline associated to the region) will be represented via adjusted posterior medians for each of the Treatment Arms, as well as their associated 95% HPD-tailed credible intervals. These results will also be presented within tabular form, and will be presented after the data have been appropriately back transformed (if applicable). The difference between the treatment arms, for the change from baseline will be represented via adjusted medians, as well as their associated 95% HPD-tailed credible intervals. These results will also be presented in tabular form, and will be presented after the data have been appropriately back transformed to give median ratios (or median differences if applicable).

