#### **8.3.4.1. Statistical Methodology Specification**

For statistical analyses of IALD in the upper and lower regions refer to Section [8.2.4.1](#) for the analysis of untrimmed siVaw but note that it is likely only 1 statistical model would be fitted for the upper and lower regions only. If appropriate this could be adapted into two models; one for upper, one for lower. The probability that the treatment ratio is greater than 1 will be presented for the lower region and the probability that the treatment ratio is less than 1 will be presented for the upper region, in addition to other values appropriately selected based on the data.

For statistical analyses of LAS at TLC in the total region only, refer to Section 8.2.4.1 for the analysis of untrimmed siVaw but note only 1 statistical model would be fitted for the Total regions only. The probability that the treatment ratio is less than 1 will be presented, in addition to other values appropriately selected based on the data.

For statistical analyses of AT at FRC in the total region only, refer to Section 8.2.4.1 for the analysis of untrimmed siVaw however it is likely that no transformation will be required for this endpoint in which case the absolute change from baseline will be fitted and probabilities that the true treatment difference is less than 1, in addition to other values appropriately selected based on the data, will also be computed for each Visit. Note only 1 statistical model would be fitted for the Total regions only.

For statistical analyses of BVD at TLC in the total region only, refer to Section 8.2.4.1 for the analysis of untrimmed siVaw but note only 1 statistical model would be fitted for the Total regions only.

For statistical analyses of siVaww at TLC in the distal region only, refer to Section 8.2.4.1 for the analysis of untrimmed siVaw but note only 1 statistical model would be fitted for the Distal regions only. The probability that the treatment ratio is less than 1, in addition to other values appropriately selected based on the data will be presented.

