2.56.	All Subjects	Refer to: PII116678/final/ Table 2.60 Note: there will be less regions	Summary of Statistical Analysis for IALD (%), for Upper and Lower Regions	Ensure no overlapping information across pages for each Region No longitudinal endpoints Footnote to include the statistical analysis conducted, including covariates, co-variance matrix and prior assumptions. Footnote any transformations used Footnote baseline	SAC
2.57.	All Subjects	Refer to: PII116678/final/ Table 2.66 Note: there will be less regions	Summary of Statistical Analysis for AT (% of iVlobe), for Total Region at FRC	Ensure no overlapping information across pages for each Region No longitudinal endpoints Footnote to include the statistical analysis conducted, including covariates, co-variance matrix and prior assumptions. Footnote any transformations used Footnote baseline	SAC
2.58.	All Subjects	Refer to: PII116678/final/ Table 2.72 Note: there will be less regions	Summary of Statistical Analysis for BVD (% of iVlobe), for Total Region at TLC	Ensure no overlapping information across pages for each Region No longitudinal endpoints Footnote to include the statistical analysis conducted, including covariates, co-variance matrix and prior assumptions. Footnote any transformations used Footnote baseline	SAC

Efficacy: Tables					
No.	Population	IDSL / TST ID / Example Shell	Title	Programming Notes	Deliverable
2.59.	All Subjects	Refer to: PII116678/final/ Table 2.84 Note: there will be less regions	Summary of Statistical Analysis for siVaww (mL/L), for Distal Region at TLC using Untrimmed Data	Ensure no overlapping information across pages for each Region No longitudinal endpoints Footnote to include the statistical analysis conducted, including covariates, co-variance matrix and prior assumptions. Footnote any transformations used Footnote baseline	SAC
Lung Function					
2.60.	All Subjects	PII115119/ Part_A /Table 3.18	Summary of FEV1 (L) and FVC (L) (Absolute Values)	Summaries by Visit Footnote any transformations used	SAC
2.61.	All Subjects	PII115119/ Part_A /Table 3.19	Summary of FEV1 (L) and FVC (L) (Change from Baseline)	Summaries by Visit Footnote any transformations used Footnote Baseline	SAC

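### The only siVaww model uses untrimmed scans, so its treatment ratio mixes wall-volume change with change in the set of visible airways; a scan-trimmed model should be pre-specified beside it

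*SAP*

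**What the plan says.** Section 8.3.2 introduces an exclusive list of exploratory HRCT models ("note: statistical analyses will only be conducted on"), in which the siVaww entry is "siVaww untrimmed data at TLC for distal region only". The same section repeats it: "For the endpoint siVaww, a statistical model will be fitted for the distal region using untrimmed data". The display list agrees; Table 2.59 is titled "Summary of Statistical Analysis for siVaww (mL/L), for Distal Region at TLC using Untrimmed Data". Section 8.3.4.1 refers the method to the untrimmed siVaw analysis in 8.2.4.1 and names the result to report: "The probability that the treatment ratio is less than 1, in addition to other values appropriately selected based on the data will be presented".

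Section 8.2.2 defines the two kinds of data. For untrimmed data: "The untrimmed data measures all airways that are present in each scan". It warns that "it can be that some airways are visible in some scans and not in other scans", partly because of positioning. For that reason some "imaging endpoints will be calculated to include only airways that are visible in both scans", which keeps the airway models the same length at both scans of a pair.

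Table 2 of section 8.2.2 shows siVaww captured both untrimmed and scan-trimmed for all three pairs, at TLC only. Display Tables 2.45 to 2.48 summarise siVaww without the note, carried by the tables for lobe volume and several other endpoints, that scan-trimmed results do not exist. Trimmed siVaww can therefore appear there descriptively.

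**The concern.** Wall volume depends on how much airway is counted. If a scan shows more of the tree than the baseline scan did, untrimmed wall volume rises even when no wall has changed; if it shows less, it falls. The SAP recognises this for airway measures generally and created trimmed data to deal with it. It then models siVaww, alone among the modelled airway-tree measures, with no trimmed version: siVaw has untrimmed and trimmed models, and siRaw has a trimmed model.

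At stake is the meaning of the reported posterior probability. A ratio below 1 would naturally be read as less airway wall on active than on placebo. From untrimmed data alone, that reading cannot be separated from fewer airways having been visible.

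**Working it through.** The SAP gives no effect size, SD or power for siVaww, so there is no figure of its own to reproduce.

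**Does the derivation remove the visibility effect?** Section 13.6.3 builds distal wall volume as the sum of the upper and lower lobe values (iVaww LL + iVaww UL) and divides it by total lobe volume. The division adjusts for lung size. It does not adjust for how many airways were seen.

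**Is there another check on it?** The sensitivity analysis attached to the untrimmed model in 8.2.4.1 concerns only bronchodilator use in the 4 hours before the scan. No comparison of trimmed with untrimmed models is specified for siVaww.

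**How do the airway-tree measures compare?**

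| Measure | Untrimmed model | Trimmed model |
|---|---|---|
| siVaw (FRC) | lobes; five regions | distal |
| siRaw (FRC) | none | distal |
| siVaww (TLC) | distal | none |

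**Size if visibility differs by arm (illustration).** Let r be the same-airway wall-volume ratio, active to placebo, and v the active-to-placebo ratio of the change in wall volume due to visibility alone. Then

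untrimmed ratio = r × v,

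and the direction reverses for r < 1 once v exceeds 1/r. All values of r and v are assumptions.

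| r | v at which the ratio reaches 1 | untrimmed ratio at v = 1.10 | at v = 1.15 |
|---|---|---|---|
| 0.80 | 1.250 | 0.880 | 0.920 |
| 0.90 | 1.111 | 0.990 | 1.035 |
| 0.95 | 1.053 | 1.045 | 1.092 |
| 0.98 | 1.020 | 1.078 | 1.127 |

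In the other direction, r = 1.05 with v = 0.90 gives 0.945: thicker walls would appear as a ratio below 1. Within a subject's trimmed pair the airway set is the same at both scans, so this v term drops out.

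**Size if visibility is unrelated to arm (illustration).** Take 15 subjects per arm (the SAP's approximate completer target in section 2.3), an assumed same-airway log SD of 0.10, and an assumed visibility log SD of s. Then

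SE = √(0.10² + s²) × √(2/15), and P(estimate on the wrong side of 1) = 1 − Φ(−ln r / SE).

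For r = 0.95, −ln r = 0.0513:

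| s | SE | P(wrong side) |
|---|---|---|
| 0 | 0.037 | 0.08 |
| 0.10 | 0.052 | 0.16 |
| 0.20 | 0.082 | 0.27 |
| 0.30 | 0.115 | 0.33 |

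There is no bias in the log ratio here, only loss of precision. If instead v = 1.10 with r = 0.95, the chance that the estimated ratio falls below 1 is 0.20 at s = 0.10 and 0.30 at s = 0.20, against 0.84 and 0.74 at v = 1.00.

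**The case against.** Several points on the other side are sound.

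- **Direction.** A reader might infer that the untrimmed model will give the wrong direction. The documents do not support that. Systematic reversal needs visibility to change differently by arm. The only cause the SAP names is positioning, which in a randomised double-blind trial is expected to add noise rather than bias. No visibility or wall-change figure is given.
- **Contradiction with siVaw.** A reader might also infer that airway opening would count for the drug in siVaw and against it in siVaww. The planned siVaw models are at FRC and the siVaww model is at TLC, and the SAP does not say that visibility moves together at the two volumes. Nor does section 8.3.4.1 say that a siVaww ratio above 1 counts against the drug; it only names a probability.
- **Trimmed evidence.** It is not absent. The descriptive tables can show it, so a discrepancy could be noticed. What is missing is a model and a posterior probability from matched airways.
- **Trimmed as the main model.** Trimming keeps only airways seen at both scans, so the retained set depends on post-baseline visibility and may differ by arm. Untrimmed data describe the whole visible tree without that selection. The two answer different questions, so demoting the untrimmed model is arguable rather than a correction.
- **The critical-components plan.** It captured siVaww under scan trimming only, but it is superseded and allowed later adaptation. The difference is context, not an error.

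Sections 8.3.2 and 8.3.4.1 and Table 2.59 are consistent that the model is fitted to untrimmed data, and section 8.2.4.1 allows alternative models. None of this makes the untrimmed ratio interpretable as wall change by itself.

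**Conclusion.** The point holds in a limited form. The single siVaww model cannot separate a change in wall volume from a change in the visible airways, although the SAP itself identifies the problem and already captures the data that would address it. Visibility change unrelated to arm costs precision: under the assumptions above, the chance of a wrong-direction estimate at r = 0.95 rises from 0.08 to between 0.16 and 0.33. Visibility change that differs by arm biases the ratio and would reverse it at r = 0.95 once the difference exceeds about 5.3% (1/0.95 = 1.053). Whether such a difference exists is not known from the documents, and the figures rest on assumed SDs and ratios. The consequence is confined to interpretation of an exploratory endpoint.

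**What to change.** In sections 8.3.2 and 8.3.4.1, add a scan-trimmed siVaww model for the distal region at TLC, using the Screening and Day 12 pair and the Screening and Day 28 pair. Use the scan-trimmed model form already given in 8.2.4.1 for siVaw and siRaw, and state the response as the log ratio to baseline; that section speaks of the log of the change from baseline, which should not be carried over literally. Add a matching display next to Table 2.59. Report both models side by side, and state that the probability of a ratio below 1 will be interpreted as wall change only where the two agree.

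While editing, reconcile Table 2.59's programming note, which excludes longitudinal endpoints, with its title. The critical-components plan used longitudinal for what the SAP now calls untrimmed.

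The cost is SAP wording, one additional model and one display, with no new data. The limitation to state is that only airways and subjects with both scans in a pair contribute, so the trimmed result depends on which airways remained visible after baseline.

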### **8.3.3. Population of Interest**

The secondary efficacy analyses will be based on the “All Subjects” population, unless otherwise specified.

### **8.3.4. Statistical Analyses / Methods**

Details of the planned displays are provided in [Appendix 10: List of Data Displays](#) and will be based on GSK Data Standards and statistical principles.

Unless otherwise specified, endpoints / variables defined in Section [8.3.1](#) will be summarised using descriptive statistics, graphically presented (where appropriate) and listed.

#### **8.3.4.1. Statistical Methodology Specification**

For statistical analyses of IALD in the upper and lower regions refer to Section [8.2.4.1](#) for the analysis of untrimmed siVaw but note that it is likely only 1 statistical model would be fitted for the upper and lower regions only. If appropriate this could be adapted into two models; one for upper, one for lower. The probability that the treatment ratio is greater than 1 will be presented for the lower region and the probability that the treatment ratio is less than 1 will be presented for the upper region, in addition to other values appropriately selected based on the data.

For statistical analyses of LAS at TLC in the total region only, refer to Section 8.2.4.1 for the analysis of untrimmed siVaw but note only 1 statistical model would be fitted for the Total regions only. The probability that the treatment ratio is less than 1 will be presented, in addition to other values appropriately selected based on the data.

For statistical analyses of AT at FRC in the total region only, refer to Section 8.2.4.1 for the analysis of untrimmed siVaw however it is likely that no transformation will be required for this endpoint in which case the absolute change from baseline will be fitted and probabilities that the true treatment difference is less than 1, in addition to other values appropriately selected based on the data, will also be computed for each Visit. Note only 1 statistical model would be fitted for the Total regions only.

For statistical analyses of BVD at TLC in the total region only, refer to Section 8.2.4.1 for the analysis of untrimmed siVaw but note only 1 statistical model would be fitted for the Total regions only.

For statistical analyses of siVaww at TLC in the distal region only, refer to Section 8.2.4.1 for the analysis of untrimmed siVaw but note only 1 statistical model would be fitted for the Distal regions only. The probability that the treatment ratio is less than 1, in addition to other values appropriately selected based on the data will be presented.

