
 
• The data will be inspected during statistical analysis to determine whether a data transformation is required. It is likely no transformations will be required
 
• The analysis will include all available values. If there are values which were recorded within 4h after the subject had taken relief medication, a sensitivity analysis may be done which excludes these values.
 
• The endpoints (FEV1 and FVC) will be analysed in separate models. The change from baseline in the endpoint will be analysed in a Bayesian repeated measures model, with a baseline by Visit covariate and Treatment by Visit class parameter. Note that the model will not include an intercept. The Treatment will have two levels: All NEMI and All Placebo, and the Visit will have two levels: Day 28 and Day 84. No fixed assumption around the structure of the covariance matrix will be enforced. The priors for the mean vector for each of the parameters (i.e. covariates) will each follow a normal distribution and the prior for the variance-covariance will follow an inverse Wishart distribution. Sensitivity analysis will be conducted to select appropriate parameters for both distributions such that the priors are non-informative with respect to the posterior.
 
• The change from baseline at each of the Visits will be represented via adjusted posterior medians for each of the Treatment Arms, as well as their associated 95% HPD-tailed credible intervals. These results will also be presented in a tabular format.
 
• The difference between the treatment arms, for the change from baseline will be represented via adjusted posterior medians for each of the Treatment Arms, as well as their associated 95% HPD-tailed credible intervals. These results will also be presented in tabular format.
 
• The probabilities that the treatment difference is greater or less than 0 (depending on direction of the endpoint), in addition to other values appropriately selected based on the data, will also be computed for each Visit. These results will be presented in tabular format.
 

Model Checking & Diagnostics

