#### Pharmacodynamic and Biomarker

##### Pharmacodynamic

##### PMNs Differentials

- Percentage data may be arc-sine transformed especially if many of the percentage values are smaller than 20% or larger than 80%. The response variable,  $y$ , measured in radians, is  $\sin^{-1}\sqrt{0.01*p}$  where  $p$  is the differential percentage.
- If transformations are used then the results will be reported on the back-transformed scale, except where a transformed value:
  - exceeds  $0.01*p/2$  then the back-transformed value will be set equal to 100%
  - is less than 0 then the back-transformed value will be set equal to 0%.

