**13.7.2.1. Handling of Missing and Partial Dates**

Element	Reporting Detail
General	
 
Partial dates will be displayed as captured in subject listing displays.
 

Adverse Events	
 
The eCRF allows for the possibility of partial dates (i.e., only month and year) to be recorded for AE start and end dates; that is, the day of the month may be missing. In such a case, the following conventions will be applied for calculating the time to onset and the duration of the event:                             
 
Missing Start Day: First of the month will be used unless this is before the start date of study treatment; in this case the study treatment start date will be used and hence the event is considered On-treatment as per Appendix 4: Study Phases and Treatment Emergent Adverse Events.
 
Missing Stop Day: Last day of the month will be used, unless this is after the stop date of study treatment; in this case the study treatment stop date will be used.
 
 
 
Completely missing start or end dates will remain missing, with no imputation applied. Consequently, time to onset and duration of such events will be missing.
 

Concomitant Medications/ Medical History	
 
Partial dates for any concomitant medications recorded in the CRF will be imputed using the following convention:                             
 
If the partial date is a start date, a '01' will be used for the day and 'Jan' will be used for the month
 
If the partial date is a stop date, a '28/29/30/31' will be used for the day (dependent on the month and year) and 'Dec' will be used for the month.
 
 
 
The recorded partial date will be displayed in listings.
 

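### Three rules outside the primary analysis are wrong as written (the air-trapping probability cut-off, the arcsine cap for PMN differentials, the adverse-event stop-day imputation), and both FEV1 percent-predicted equations are mislabelled

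*SAP*

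**What the plan says.** **Air trapping.** Section 8.3.2 expects that "no transformation will be required for Percent Predicted iVlobe and AT". Section 8.3.4.1 then says that "the absolute change from baseline will be fitted and probabilities that the true treatment difference is less than 1" will be computed at each visit, together with unnamed further values chosen from the data. In the same section the value 1 is used for the ratio endpoints IALD, LAS and siVaww. It is also the value used for the treatment ratio in the log-scale siVaw model of Section 8.2.4.1, to which the AT text refers. For FEV1 and FVC, which are analysed as differences, Section 8.1.4.1 uses 0: "The probabilities that the treatment difference is greater or less than 0 (depending on direction of the endpoint".

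**PMN differentials.** Section 13.6.5 makes a transformation optional: "Percentage data may be arc-sine transformed especially if many of the percentage values are smaller than 20% or larger than 80" per cent. The transformed value is arcsin(sqrt(0.01p)), with p the differential percentage. If a transformed value exceeds 0.01*p/2, "then the back-transformed value will be set equal to 100" per cent. A value that "is less than 0 then the back-transformed value will be set equal to 0" per cent.

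**Adverse-event stop day.** In Section 13.7.2.1 a missing stop day becomes the last day of the month, "unless this is after the stop date of study treatment; in this case the study treatment stop date will be used". For concomitant medication the same section has no such cut: "If the partial date is a stop date, a '28/29/30/31' will be used for the day". Section 13.4.2 defines AE duration as resolution date minus onset date plus 1, and has a post-treatment category for events that start after treatment stop.

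**FEV1.** Section 13.6.3 gives one equation for men and one for women, both labelled FEV1 percent predicted. They contain only height and age.

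**The concern.** For AT, the named probability appears to carry the null value of a ratio onto a difference scale. It would then not measure evidence that AT falls, and Table 2.57 would lean towards benefit where there is none. For PMN differentials, the upper guard should be the maximum of the transform, but the printed expression depends on p and looks far too small. For adverse events, cutting the stop date back to treatment stop shortens events that outlast treatment, and for events that begin after treatment it can put the stop before the onset. AE review takes place at a follow-up visit 7 to 14 days after the last dose (Section 13.2.1), so such events are to be expected. The FEV1 label invites a programmer to report litres as a percentage.

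**Working it through.** The plan gives no figure of its own to reproduce here, so each rule is applied literally.

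**1. Air trapping.** The document gives no SD for the change in AT, so SDs of 3, 5, 8 and 10 percentage points are assumed. Two illustrative sizes are used: 15 per arm (the completer target in Section 2.3) and 22 per arm (about half of the 45 to be randomised). With vague priors the posterior for the difference is taken as approximately normal, with SE = SD x sqrt(2/n). At an estimate of 0, P(difference < 1) = Phi(1/SE), while P(difference < 0) = 0.50.

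| SD | SE, n = 15 | P(diff < 1) | SE, n = 22 | P(diff < 1) |
|---|---|---|---|---|
| 3 | 1.095 | 0.82 | 0.905 | 0.87 |
| 5 | 1.826 | 0.71 | 1.508 | 0.75 |
| 8 | 2.921 | 0.63 | 2.412 | 0.66 |
| 10 | 3.651 | 0.61 | 3.015 | 0.63 |

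The rule can also hide harm. With a posterior mean of +0.5 points and a posterior SD of 2, P(difference < 1) is 0.60 while P(difference < 0) is 0.40.

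**2. PMN cap.** The transform arcsin(sqrt(0.01p)) is set against the stated cap 0.01p/2.

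| p (%) | Transformed value | Cap |
|---|---|---|
| 1 | 0.100 | 0.005 |
| 20 | 0.464 | 0.10 |
| 50 | 0.785 | 0.25 |
| 80 | 1.107 | 0.40 |
| 100 | 1.571 | 0.50 |

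Over 0 < p <= 100 the smallest ratio of transformed value to cap is 2.76, at p = 84.5, so the cap is exceeded by every non-zero percentage. For a mean or a confidence limit p is not defined, so the cap has no stated value there. If p is a pi lost in typesetting, the cap is 0.01 x pi/2 = 0.0157, which back-transforms to 100 x sin²(0.0157) = 0.025%, so that reading does not rescue it. The maximum of the transform is pi/2 = 1.5708, and no percentage up to 100 exceeds it.

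**3. AE duration.** For an onset k days after treatment stop, when the end of the stop month is later than treatment stop, the imputed stop is the treatment stop date. Duration is then stop - (stop + k) + 1 = 1 - k. The dates below are illustrative, with the stop recorded only as June.

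| Last dose | Onset | Duration under the rule | Duration to month end |
|---|---|---|---|
| 15 June | 10 June | 15 - 10 + 1 = 6 | 30 - 10 + 1 = 21 |
| 15 June | 16 June | 15 - 16 + 1 = 0 | 30 - 16 + 1 = 15 |
| 15 June | 20 June | 15 - 20 + 1 = -4 | 30 - 20 + 1 = 11 |
| 28 May | 5 June | -8 + 1 = -7 | 30 - 5 + 1 = 26 |

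In the last row the imputed stop, 28 May, also lies outside the recorded month.

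**4. FEV1.** The heights and age are illustrative. Man of 1.75 m aged 65: 4.30 x 1.75 - 0.029 x 65 - 2.49 = 3.15. Woman of 1.62 m aged 65: 3.95 x 1.62 - 0.025 x 65 - 2.60 = 2.17. These are predicted litres. No measured FEV1 enters, so neither can be a percentage of predicted.

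**The case against.** The arithmetic is not in dispute. The case against is about weight.

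- **AT** is exploratory, and the untransformed analysis is only described as likely. Further cut-offs may be added, and Section 8.3.2 also calls for the median difference with its 95% HPD interval, which shows no effect at 0 directly. The SDs above are assumed, the SE ignores the baseline covariate, and 15 per arm is a sputum-completer target and not a scan count. All of this is fair. But the result exceeds 0.5 at a null estimate for any SD, and permission to add values chosen from the data does not fix the null in advance.
- **The PMN transformation** is optional, the PMN displays (Tables 6.6, 6.7, 6.10 and 6.11) are descriptive, and such a guard matters mainly for computed limits that leave the valid range. A programmer would probably notice 1% printed as 100%. That lowers the risk, but the rule is unusable either way: wrong for individual values and undefined for means and limits.
- **The AE rule** acts only on missing stop days where month end is later than treatment stop. No AE table (3.1 to 3.6) is titled duration, and listings show partial dates as recorded. Ending an on-treatment event at treatment stop could be defended as a convention; a zero or negative duration, or a stop outside the recorded month, could not. It is also true that month-end imputation could run past death or last contact, so a limit there may be worth adding.
- **The FEV1 point** is a label. No listed display is titled percent predicted, and the FEV1 and FVC models use litres. It would not merit a comment alone, but Section 1 records that percent predicted will be calculated in house, so the formula should be written correctly.

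**Conclusion.** The concern holds. The AT cut-off, the PMN cap and the AE stop-day rule give wrong output if followed as written, and the two FEV1 equations carry the wrong label. The AT cut-off matters most, because it fixes the only named probability in a planned display. It overstates evidence of a reduction by 0.11 to 0.37 at a null estimate, under the assumed SDs of 3 to 10 points and 15 or 22 per arm; the direction needs no assumption. The PMN error is total for individual percentages, but only if the option is used. The AE error affects the derived duration and any listing that shows it. The primary mRNA analysis, the secondary efficacy models and treatment-emergent status, which depends on the start date, are unaffected. These are corrections that should be made, not reasons to doubt the main results.

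**What to change.** 1. Section 8.3.4.1: for untransformed AT, name the probability that the treatment difference is below 0, in line with Section 8.1.4.1. If 1 percentage point is meant as a margin, say so, justify it, and report it alongside 0.
2. Section 13.6.5: replace the cap 0.01*p/2 by pi/2.
3. Section 13.7.2.1: remove the treatment-stop cut for adverse events. Impute a missing stop day as the last day of the recorded month, never before onset and never outside that month.
4. Section 13.6.3: relabel both equations as predicted FEV1 in litres, and define percent predicted as 100 x measured FEV1 / predicted FEV1.

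Each change is one line of text and needs no new data.
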